We will enroll eligible prostate patients who were diagnosed between 2010 and 2019 and are being followed within radiation and medical oncology clinics at the MedStar Georgetown University Hospital (MGUH) and MedStar Washington Hospital Center (MWHC). In this initial pilot, we will not focus on newly diagnosed patients but instead will focus on patients who are being followed for a number of reasons: 1) Substantial numbers of patients who are currently being followed have now become candidates for genetic testing based on updated guidelines and 2) This will allow us to maximize our potential sample size within the one year framework of this grant, allowing us to obtain preliminary efficacy data in preparation for a planned multisite R01 study of newly diagnosed patients with high risk localized or metastatic disease. By providing information particularly salient to prostate cancer patients, reducing barriers to genetic testing and proactively facilitating genetic testing delivery, we expect that our proactive and streamlined approach will yield increased uptake of genetic testing. Our specific aims are:

- 1: **Evaluate the impact of ST vs. UC on genetic testing uptake.** *H1.1:* Patients randomized to ST will be more likely to complete genetic testing compared to UC. *H1.2:* Participants randomized to ST will make better informed genetic testing decisions (characterized by high knowledge, risk comprehension and concordance with attitudes) compared to UC. *H1.3:* Few patients in the ST arm will opt for traditional genetic counseling prior to testing.
- 2: **Evaluate patient satisfaction and psychosocial outcomes in ST vs. UC.** *H2.1:* Compared to UC, those randomized to ST will be more satisfied with their genetic testing decision and will have less decisional regret.
- 3: **Evaluate the impact of ST vs. UC on uptake of cascade testing in unaffected family members.** In exploratory analyses designed to provide effect size estimates, we will compare the arms on rates of genetic testing in relatives of patients found to carry a PV.

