### 3.0 Background\*

**Germline Genetic Testing in Prostate Cancer.** Up to 17% of men with prostate cancer have an inherited PV in a cancer gene. For many of these men, this knowledge may impact their medical management. Prostate cancer patients with *BRCA* PV develop higher risk disease than non-carriers. Prostate cancer patients with a *BRCA* PV with localized disease have more frequent nodal involvement, higher Gleason scores, more T3/T4 disease and lower cause specific overall survival at 5 years. Men with metastatic castration-resistant prostate cancer have significantly shorter cause specific overall survival in *BRCA2* carriers vs. non-carriers. The use of single agent PARP inhibitors in patients with *BRCA* PVs and metastatic castration-resistant prostate cancer was associated with high rates of response, leading the FDA to grant breakthrough therapy designation for olaparib and rucaparib in patients with *BRCA* positive metastatic castration resistant prostate cancer. NCCN guidelines suggest germline testing in patients with castration resistant metastatic prostate cancer to guide the early use of platinum chemotherapy as well as for eligibility for clinical trials using PARP inhibitors. In addition, prostate cancer patients with localized Gleason Grade 7+ prostate cancer are recommended to consider genetic testing if they have a family history of breast, ovarian, pancreatic or prostate cancer or are of Ashkenazi Jewish ancestry, regardless of family history. All prostate cancer patients with a *BRCA* PV are at increased risk for second malignancy (e.g., pancreatic cancer, male breast cancer, melanoma). The identification of a PV in a prostate cancer patient also has important

implications for his male and female family members who can use test results to guide their cancer risk reduction and management decisions. *Thus, the identification of a PV in a prostate cancer patient may often have treatment and risk management implications for the patient and his unaffected family members.*

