Recruitment. Working with our clinical collaborators and the Survey, Recruitment and Biospecimen Collection Shared Resource (SRBSR) will obtain contact information of potentially eligible patients from clinical databases and/or the EMR. We will mail an introductory letter describing the study (from the study MPIs and the patient's physician), opt-out postcard/phone number, informed consent document and a print version of the baseline survey to all potentially eligible participants. We will also email electronic versions of these materials for patients who prefer to complete them online. Two-weeks following this mailing, an SRBSR research assistant (RA) will call patients who have neither opted out nor completed the baseline survey. For men who have not returned the consent document, we will use an IRB-approved verbal consent for completing the baseline survey and request return of the written consent prior to randomization. Following completion of print or electronic consent and the baseline survey, the RA will randomize participants. Men randomized to ST will be sent a priority mail packet with detailed genetic testing educational material. Men randomized to UC will be mailed a letter informing them that they meet guidelines for genetic counseling and provided with contact information to schedule a genetic counseling appointment with a LCCC genetic counselor.

Randomization. Following completion of the baseline survey and consent document, an RA will randomize participants via computer-generated random numbers in blocks of 8 and a ratio of 1:1. Participants will be notified of their random assignment via letter and email.

**Assessments.** We will administer baseline (T0) and 2- to 3-month (T1) follow-up telephone/electronic surveys. Genetic testing uptake will be assessed via clinical records and basic clinical and demographic information abstracted from the EMR. See Table 1 for assessment instruments and schedule of administration.

Table 1. Measures		T0	T1
Variables	Measures		
Covariates/Background Variables	Demographics, clinical variables, family history (EMR/survey)	X	
Health Literacy	Brief Health Literacy Screening Tool	X	
Genetic Test Uptake	Study Records		X
Knowledge/Risk Comprehension	Genetic Knowledge Scale and Perceived Mutation Risk.	X	X
Attitudes	Adapted version of the Multimodal Measure of Informed Choice (MMIC), Fatalism, Medical Mistrust Index	X	
Decision Regret	Decisional-Regret Scale.		X

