## **17.0 Data Management\* and Confidentiality**

*17.1* Data Analysis: We will characterize participants by comparing them to decliners on key demographic and clinical variables derived from the EMR. After performing univariate analysis on dependent variables, we will apply any needed normalizing or variance stabilizing transformations. We will follow Consort guidelines for Intent-to-Treat analyses (ITT). We will compare groups at baseline with  $\chi^2$  and t-tests and will include covariates that are associated with group ( $p < 0.10$ ) in our final models.

**Aim 1: Evaluate the impact of Proactive Streamlined Education and Testing (ST) vs. Usual Care (UC) on genetic testing.** Analysis: H1.1: Patients randomized to ST will be more likely to complete genetic testing compared to UC. We will use logistic regression to test this hypothesis. After entering significant covariates, we will add intervention arm to test the overall intervention effect. H1.2: Participants randomized to ST will make better informed genetic testing decisions (characterized by high knowledge, risk comprehension and positive attitudes) compared to UC. Using multiple regression, we will enter control/confounding variables and intervention to test the impact of group on our informed decision making outcomes (knowledge, testing attitudes, risk comprehension). H1.3: Few patients in the ST arm will opt for traditional genetic counseling prior to testing. We will conduct descriptive analyses describing the proportion of ST participants who opt for genetic counseling vs. proceed directly to testing vs. opt against testing.

**Aim 2: Evaluate patient satisfaction and psychosocial outcomes in ST vs. UC.** Analysis: H2.1: Compared to UC, those randomized to ST will be more satisfied with their genetic testing decision and will have less decisional regret. After identifying baseline confounders of each outcome, we will generate linear regression models in which we enter: 1) confounders; 2) genetic test result (dummy

coded to generate comparisons of carriers vs. non-carriers and non-carriers vs. untested); 3) group assignment. In the event that we have an insufficient number of PV carriers for these analyses, we will categorize test result into two levels (tested vs. untested) and evaluate results among PV carriers more descriptively. Results of Aim 2 analyses will be primarily focused on generating effect size estimates for our planned trial of newly diagnosed prostate cancer patients.

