**Aim 3: Evaluate the impact of ST vs. UC on uptake of cascade testing in unaffected family members.** In exploratory analyses designed to provide effect size estimates for our planned R01, we will use t-test to compare the ST to UC on the number of relatives of PV carriers who undergo cascade genetic testing.

**Power:** Power estimates are for 2-tailed tests ( $\alpha=.05$ ). The study is powered based on our primary outcome of patient genetic testing uptake. We expect no attrition since data will be abstracted from clinic records. With no relevant studies on which

Table 2. Sample Size Calculation			
	ST Uptake		
UC Uptake	.40	.45	.50
10%	39	25	20
15%	49	36	27
20%	81	54	39

to base our effect sizes for this pilot study, Table 2 displays the necessary sample size (per group) to obtain 80% power for a range of potential clinically significant effects on test uptake (40%-50% for ST; 10%-20% for UC). Based on this analysis, we will enroll 120 participants in order to attain 80% power to detect a clinically meaningful difference between 20% in UC and 45% in ST. For our secondary outcomes, a sample size of 120 and 10% attrition at 3-months (n=108 in final sample) will provide  $> 80\%$  power to detect medium sized effects of  $d=.54$  SDs on our secondary outcomes (e.g., decisional conflict, patient satisfaction). This effect size is well within the range that we have seen in previous studies and represents an effect that is generally considered to be clinically significant.

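### The only H2.1 model adjusts for genetic test result, which ST is meant to change, so it does not estimate the randomised ST-versus-UC effect; the Aim 3 t-test rests on very few carriers, identified after randomisation

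*Combined protocol and SAP*

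**What the plan says.** H2.1 in section 2.0 is a plain comparison of the randomised arms: "Compared to UC, those randomized to ST will be more satisfied with their genetic testing decision and will have less decisional regret". Section 17.1 repeats it.

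The only analysis given for it is the Aim 2 linear regression in 17.1. Confounders go in first, then test result, "coded to generate comparisons of carriers vs. non-carriers and non-carriers vs. untested); 3) group assignment". If there are too few carriers, "we will categorize test result into two levels (tested vs. untested"), so a testing term stays in the model either way. No H2.1 model without that term appears anywhere.

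The purpose is stated in the same paragraph: "Results of Aim 2 analyses will be primarily focused on generating effect size estimates for our planned trial". The sample size in 17.1 is set "to detect a clinically meaningful difference between 20% in UC and 45% in ST" on test uptake, so the plan itself expects arm to change testing. For secondary outcomes it assumes "a sample size of 120 and 10% attrition at 3-months (n=108 in final sample").

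For Aim 3, section 17.1 applies a t-test to the number of relatives tested among PV carriers. It is labelled exploratory and is also meant to give effect sizes for the planned R01. The carrier rate in section 3.0 is "Up to 17% of men with prostate cancer have an inherited PV in a cancer gene".

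**The concern.** Test result, including the untested category, is determined after randomisation, and changing it is the purpose of ST. Once it is in the model, the arm coefficient compares ST and UC men with the same testing outcome. Any gain or loss in satisfaction that comes from more men being tested is taken out. The tested-versus-untested fallback does not help, because uptake is exactly what ST moves.

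A second problem is possible: an unmeasured trait that drives both testing and satisfaction would bias the adjusted coefficient further. This is limited, because Table 1 in section 6.0 measures several candidates at T0 ("Adapted version of the Multimodal Measure of Informed Choice (MMIC), Fatalism, Medical Mistrust Index") and they can enter as baseline covariates.

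Nobody is excluded, so this is not a breach of the intention-to-treat commitment. It is a mismatch between hypothesis and model. It matters because the estimate is Aim 2's main product, and the direction of the error cannot be known in advance.

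Aim 3 has a related but smaller problem. Germline status is fixed before randomisation, but a carrier is detected only if he is tested, and that depends on arm. The comparison among detected carriers is therefore not a randomised one, and it rests on very few men.

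**Working it through.** **Inputs from the documents.** Uptake 20% UC and 45% ST; Table 2 range 10% to 20% UC and 40% to 50% ST; 120 men at 1:1, so 60 per arm; 108 with T1 data, so 54 per arm; d = 0.54 SD for secondary outcomes; PV rate up to 17%. **Assumptions (not in the documents).** The direct effect of ST, the effect g of testing on the outcome in SD, the strength of any shared cause, and the 10% PV rate used as an alternative.

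**1. The plan's own figures.** With n per arm = 2(1.960 + 0.842)²/d², d = 0.54 gives 54 per arm. Power at 54 per arm is 80.1% by the normal approximation (79.4% by noncentral t). The secondary-outcome power statement thus reproduces, to within rounding, as a simple two-group comparison, which the H2.1 model is not. The primary figure of 54 per group for 20% versus 45% also reproduces.

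**2. What the H2.1 model estimates.** Randomised effect = direct effect + (0.45 - 0.20) × g. With no unmeasured shared cause and no arm-by-testing interaction, the planned model returns the direct effect only. Take a direct effect of 0.20 SD:

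| g (SD) | Randomised effect | Planned model | n per arm, 80% power, from randomised effect |
|---|---|---|---|
| -0.25 | 0.20 - 0.0625 = 0.1375 | 0.20 | 831 |
| +0.25 | 0.20 + 0.0625 = 0.2625 | 0.20 | 228 |
| +0.50 | 0.20 + 0.125 = 0.325 | 0.20 | 149 |
| +0.75 | 0.20 + 0.1875 = 0.3875 | 0.20 | 105 |

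Sizing on 0.20 gives 393 per arm in every row. The three-level coding (carrier, non-carrier, untested) behaves the same way: it also returns about 0.20, with g read as the average effect of being tested.

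Across Table 2 the uptake difference runs from 20 points (40% - 20%) to 40 points (50% - 10%). The part removed is then 0.10 to 0.20 SD at g = +0.50, and 0.05 to 0.30 SD over g = +0.25 to +0.75.

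**3. Starting from the plan's d = 0.54.** If that is the randomised effect and g = 0.50, the planned coefficient is 0.54 - 0.125 = 0.415. The correlation of arm with testing is 0.27, a variance inflation of 1.077. Power at 54 per arm falls from 80% to 55%. With g = 0, only the variance inflation acts and power is 77%.

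**4. Shared cause of testing and satisfaction.** Simulation of 4,000,000 men, uptake held at 20% and 45%, direct effect 0.20, g = +0.50, and a standard-normal trait that raises both testing and the outcome:

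| Trait effect per SD | Arm only | Arm + tested | Arm + tested + trait |
|---|---|---|---|
| none | 0.325 | 0.200 | 0.200 |
| log-odds 0.5; 0.2 SD | 0.325 | 0.176 | 0.200 |
| log-odds 1.0; 0.4 SD | 0.325 | 0.116 | 0.200 |

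With no effect of ST or testing, the planned model returns -0.024 and -0.084 if the trait is unmeasured, and 0.000 if it is adjusted for.

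**5. Scale against sampling error.** At n = 108 the SE is 2/√108 = 0.192 SD, or 0.192 × √1.077 = 0.200 with the testing term. The shift for g from +0.25 to +0.75 at the planned uptake is 0.0625 to 0.1875 SD, at most about one SE.

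**6. Aim 3 carriers.** Detected carriers per arm are Binomial(60, uptake × PV rate).

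| | PV 17% | PV 10% (assumed) |
|---|---|---|
| Expected UC | 60 × 0.20 × 0.17 = 2.04 | 1.2 |
| Expected ST | 60 × 0.45 × 0.17 = 4.59 | 2.7 |
| P(UC has none) | 12.5% | 30% |
| P(UC has at most one) | 39% | 66% |
| P(both arms have two or more) | 58% | 26% |

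A t-test of 5 against 2 men would need a difference of about 2.9 SD for 80% power.

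**The case against.** The strongest reply is that conditioning may be deliberate. The outcomes concern the testing decision, and comparing arms among men who made the same decision is a legitimate question. That supports keeping the model under its own label. It does not make it the analysis of H2.1 as worded, and no unconditional model accompanies it.

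The magnitudes are also open to challenge. The documents give neither a direct effect of 0.20 SD nor a value for g, and small effects exaggerate sample-size contrasts. Starting from 0.54 with g = 0.50, the next trial would be sized at 92 per arm instead of 54, an error towards a larger trial. Sampling error is large too: an estimate of 0.20 with SE 0.20 has a 95% interval of about -0.19 to 0.59. The plan does not say that this coefficient alone will size the next trial. All of this stands, so the sample-size contrasts are illustrations. The change of estimand does not depend on them.

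On Aim 3, the analysis is labelled exploratory. A pooled t-test can be computed with one carrier in an arm, and at 17% both arms have at least one with about 87% probability. The 17% refers to men with prostate cancer generally and is not a proven ceiling for men who meet referral criteria. At an assumed 25% the expected counts are 3.0 and 6.8, and UC has at most one carrier with 19% probability. The test would then be very imprecise, but not impossible. A count per randomised man also partly reflects the uptake difference and departs from the section 2.0 wording about relatives of detected carriers. It does fit Aim 3's heading, which concerns the impact of ST versus UC on cascade testing.

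**Conclusion.** The concern holds. As written, the H2.1 model does not estimate the effect that H2.1 states. This follows from the model terms and the plan's own expectation that ST raises testing, and needs no assumed effect size. How far the estimate moves does depend on assumptions: 0.05 to 0.30 SD across Table 2 for a testing effect of +0.25 to +0.75 SD, with the opposite sign if testing lowers satisfaction. In this trial the shift is at most about one SE at the planned uptake. It is therefore a systematic displacement of the estimate to be carried forward, not a large error in this trial's test.

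For Aim 3, the t-test is not a randomised comparison and will often rest on two or fewer UC men. Section 17.1 foresees too few carriers for Aim 2 but gives Aim 3 no fallback.

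Severity is moderate: this should be corrected, but H1.1 and H1.2 are unaffected, Aim 2 is secondary and Aim 3 exploratory.

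**What to change.** **Aim 2.** In 17.1, make the main H2.1 model baseline covariates plus arm, in all randomised men with T1 data, analysed as assigned. Name it as the source of effect sizes for the next trial. Keep the test-result model, with its fallback, as a labelled secondary analysis of the arm difference given testing outcome. Report T1 completion by arm. Optionally, impute missing T1 scores as a sensitivity analysis; tested status is known from records and may enter the imputation model but not the analysis model.

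**Aim 3.** Report the between-arm difference in relatives tested per randomised participant, counting 0 where no PV is detected, with an exact or permutation-based interval. Use a difference, because a ratio is undefined when UC has none. State how a detected carrier without T1 data is counted. Give per-carrier counts descriptively, without a t-test.

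**Cost.** Wording in 17.1 only: no new data, no change in sample size, and no planned model lost.

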## **4.0 Study Endpoints\***

### **4.1 Primary and secondary endpoints:**

1. Genetic test uptake
2. Receipt of pre-test genetic counseling
3. Psychosocial outcomes (Satisfaction, distress, decision regret)
4. Use of cascade testing among unaffected family members of mutation carriers

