Decision Satisfaction	Satisfaction with Decision Scale.		X
Distress	Cancer distress: PROMIS Anxiety and Depression; Genetic testing distress MICRA.	X	X
Quality of Life/Functional Status	PROMIS Physical Function and Social Function Short Forms	X	X
Cascade Testing	Number of relatives who have proceeded with genetic testing.		X

**Streamlined Testing (ST) Intervention.** Men randomized to ST will be sent a priority mail packet with the ST print education materials and information on how to proceed with genetic testing. ST participants will have the option of proceeding directly to genetic testing or scheduling a telephone genetic counseling session. The content of the ST intervention is described in section 5.0 above.

**Usual Care (UC).** After completion of the baseline survey, UC participants will be sent a letter from their physician indicating that they meet eligibility criteria for genetic testing, recommending that they schedule genetic counseling and providing a contact telephone number to schedule their session. Patients may opt for free telephone genetic counseling.

**Genetic Testing.** Participants who choose to pursue genetic testing will be offered a standard clinical multigene panel of at least 40 genes, including *BRCA* and genes associated with potential differential diagnoses (e.g., Lynch syndrome). All testing will be performed by Invitae, a CLIA certified clinical lab not affiliated with the GLCCC. Invitae offers genetic testing free of charge to eligible prostate cancer patients (all study participants will be eligible for free genetic testing through Invitae). Prior to proceeding with genetic testing, participants will be required to sign and return a clinical genetic testing consent form, after which we will mail them an at-home DNA kit for saliva collection which will be returned directly to Invitae (shipping costs are pre-paid).

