**9.0** **Study Timelines\***

*9.1* Participants will remain in the study for 3 months after randomization.

We expect participant enrollment to be completed within three-months.

The anticipated study completion date is 9/1/20.

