## 25.0 Resources Available

25.1 *Recruiting Feasibility:* Men eligible for this study are currently being followed at MGUH or MWHC for metastatic prostate cancer or Gleason 7+ prostate cancer with a family history of breast, ovarian, pancreatic or prostate cancer or Ashkenazi Jewish ancestry. We will exclude patients who have had or are scheduled for, genetic counseling or testing. We will also exclude men who cannot participate in English and provide meaningful consent. We will recruit participants from medical and radiation oncology clinics at MGUH and MWHC (see letters of

support in attached protocol). These clinics currently follow well over 1000 eligible patients. Although we routinely attain 70% case participation, we can attain our required sample size (n=120) with much lower rates of participation.

*Time:* The project will be conducted over the next year with data analysis and manuscript preparation continuing for 1 years after the completion of participant follow-up.

*Facilities:* Participants will be contacted via mail, telephone and electronically. The study staff will initiate these contacts from the Cancer Prevention and Control office suite and from the offices of SRBSR in MGUH. Each member of the study staff has a private or semi-private office with private telephone and private secured workstations. Each office is locked and accessible only by the study staff member and the PI or Project Director. All DNA will be collected using standard DNA saliva kits used by the study participants in the privacy of their home. DNA will be shipped by mail to the designated commercial genetic testing company for preparation and sequencing in a secure and CLIA-approved facility as is standard for all clinical genetic testing samples.

*Medical and Psychological Resources:* This is a low-risk study. However, all participants will have access to a board-certified genetic counselor. All of these counselors are trained and experienced at recognizing signs of psychological distress. All positive genetic test results will be delivered by a board-certified genetic counselor who will assess psychological reactions to genetic test results and make referrals for additional services as needed. All negative or VUS results will be delivered via mailed clinical letter and will include contact information for the assigned genetic counselor in case the participant wishes to schedule a session.

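### Aim 3 compares cascade testing only among men found to carry a PV, a group formed after randomisation by testing uptake, so its effect estimate omits the main documented route by which ST could reach more relatives

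*Combined protocol and SAP*

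**What the plan says.** Section 2.0 gives Aim 3 as "Evaluate the impact of ST vs. UC on uptake of cascade testing in unaffected family members" and adds that "we will compare the arms on rates of genetic testing in relatives of patients found to carry a PV". Section 4.1 lists the endpoint as "Use of cascade testing among unaffected family members of mutation carriers". In section 17.1 the analysis is that "we will use t-test to compare the ST to UC on the number of relatives of PV carriers who undergo cascade genetic testing". Both sections call Aim 3 exploratory and give its purpose as effect-size estimates for the next trial.

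Table 1 in section 6.0 has one cascade item, "Number of relatives who have proceeded with genetic testing", marked at T1 only. T1 is the follow-up survey 2-3 months after randomisation, and section 9.1 says "Participants will remain in the study for 3 months after randomization". No later follow-up of relatives is described.

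Section 17.1 also commits the trial to intent-to-treat analysis. For Aim 2 it provides a fallback in case there are too few PV carriers. Aim 3, which depends wholly on carriers, has none.

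**The concern.** The title of Aim 3 asks what ST does to cascade testing. The analysis asks something narrower: among men already found to carry a PV, how many relatives test in each arm?

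A man enters that comparison only if he chose to be tested, which is the primary outcome. The carriers in the two arms are therefore not groups formed by randomisation. Those in UC have also gone through a scheduled pre-test counselling session, so they may differ in motivation from carriers in ST.

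Under sections 2.0 and 8.1, a PV result is disclosed in a telephone session with a genetic counsellor in both arms. The documents thus describe no difference in how carriers are handled once the result is known. The main route they offer by which ST could increase cascade testing is that more carriers are found, and conditioning on carriers removes it.

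Timing adds a second limit. T1 is counted from the patient's randomisation, not from his result. Before a relative can act on that result, the patient must decide, return the clinical consent, receive a kit, send saliva to the laboratory and have the disclosure session. UC men must first arrange and attend counselling. Relatives' observation time is therefore shorter than 2-3 months and probably shorter in UC.

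At stake is the one stated use of Aim 3. A planner who took the carriers-only difference as the effect of ST on cascade testing would carry forward an estimate that leaves out the uptake gain.

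**Working it through.** **Inputs.**
- 120 men allocated 1:1, so 60 per arm (sections 6.0 and 17.1).
- Design uptake: 45% ST, 20% UC (section 17.1, Power).
- PV rate: section 3.0 says "Up to 17% of men with prostate cancer have an inherited PV in a cancer gene". I use 17% as an upper figure; 10% and 5% are my assumptions, to show the range.
- Survey attrition of 10%, leaving 108 men or 54 per arm (section 17.1, stated for secondary outcomes). Applying it to the cascade count assumes that the count comes from the T1 survey; Table 1 names no source for this item.
- m, the mean number of tested relatives per known carrier, is not given and is left as a symbol.

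**The plan's own figure.** No figure is stated for Aim 3. The uptake calculation behind these inputs reproduces. With pooled variance, two-sided alpha 0.05 and 80% power, n = [1.96√(2 × 0.325 × 0.675) + 0.8416√(0.20 × 0.80 + 0.45 × 0.55)]² / 0.25² = 53.9, or 54 per group, as in Table 2.

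**Carriers expected.** Expected carriers = n × uptake × PV rate.
- ST: 60 × 0.45 × 0.17 = 4.59. UC: 60 × 0.20 × 0.17 = 2.04.
- With 54 per arm at T1: 4.13 and 1.84.

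**Can the t-test be run?** UC carriers are binomial with n = 60 and probability 0.20 × PV rate.

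| PV rate | Expected carriers ST v UC | P(no UC carrier) | P(at most one UC carrier) | P(two or more in each arm) |
|---|---|---|---|---|
| 17% (protocol's upper figure) | 4.59 v 2.04 | 0.13 | 0.39 | 0.58 |
| 10% (assumed) | 2.70 v 1.20 | 0.30 | 0.66 | 0.26 |
| 5% (assumed) | 1.35 v 0.60 | 0.55 | 0.88 | 0.05 |

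With no UC carrier there is no comparison. With one, the UC arm has no variance estimate of its own. Even with 5 carriers v 2, a two-sided t-test reaches 80% power only at a standardised difference of about 2.9.

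**What each comparison estimates.** Suppose m is the same in both arms.
- Carriers only: m − m = 0.
- Per randomised man, counting zero for untested men and non-carriers: ST 0.45 × 0.17 × m = 0.0765m; UC 0.20 × 0.17 × m = 0.034m. The difference is 0.0425m and the ratio 0.45/0.20 = 2.25.
- Total tested relatives: 4.59m v 2.04m.

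**Precision of the alternative.** With Poisson counts per carrier and a t-test over all 120 men, simulated power is about 1% at m = 0.25 and about 10% at m = 2. Changing the denominator corrects what is estimated. It does not turn Aim 3 into a test.

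**Time left to relatives.** The documents give no laboratory turnaround and no interval to disclosure. The time can be bounded as less than 2-3 months but not computed.

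**The case against.** The strongest reply is that the omitted effect is the Aim 1 effect. The 2.25 is simply the ratio of design uptakes, and H1.1 already compares uptake over all randomised men. Follow-through per carrier is a separate and useful quantity: do men who skipped pre-test counselling pass on their results as well as men who had it? Planners of the next trial, which will enrol newly diagnosed men with possibly different uptake, may want the components apart. This stands as a reason to keep the per-carrier figures. It does not justify presenting them alone under a heading about the impact of ST on cascade testing.

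Second, section 17.1 states no denominator, and its sentence read alone could mean a total per arm. However, section 2.0 speaks of rates in relatives of men found to carry a PV, and a t-test needs one observation per person. The carriers-only reading is the natural one. At the least, the denominator needs stating.

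Third, Aim 3 is exploratory in a pilot, and no confirmatory conclusion depends on it. That is true and limits the consequence.

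A reader might also infer from the T1 timing that cascade counts will be close to zero in both arms. The documents do not support this: they give no laboratory, disclosure or relatives' testing times. It would also cut against the main point, because the per-man difference is 0.0425m and vanishes as m approaches zero. What the documents support is observation time that is shortened by an unknown amount, with an extra step in UC.

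**Conclusion.** The point holds as a mismatch between the stated aim and its analysis. Aim 3 conditions on a post-randomisation group defined by the primary outcome, contrary to the section's own intent-to-treat commitment, and leaves out the main documented route to a benefit. At the design uptakes and the 17% upper figure, about 4.6 ST carriers would be compared with 2.0 UC carriers, with a 0.39 chance of at most one in UC; lower PV rates make this worse. Under equal follow-through, the planned contrast has expectation zero against a 2.25-fold difference per randomised man. That ratio rests on the design uptakes, the same PV rate in both arms and equal m; its absolute size depends on m, which is unknown.

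The change is worth making because an effect size for the next trial is the only stated purpose of Aim 3. The timing limit calls for a label and a caveat. It does not show that the T1 count is uninformative or that longer follow-up is essential.

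**What to change.** In section 17.1, define the Aim 3 comparison as tested relatives per randomised man, over all randomised men in the arm assigned, with zero for untested men and non-carriers. State how carriers who miss T1 are handled, since their count is unknown rather than zero. Report the rate difference with an interval instead of relying on a t-test, and say that it is descriptive. Beside it, list by arm the carriers found and the relatives tested per carrier, so that the uptake and follow-through components can be seen separately. Align the wording in sections 2.0 and 4.1. In Table 1, label the T1 count as early uptake.

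This is a wording change that uses data already planned for collection. The downside is that the per-man estimate is imprecise and partly repeats the Aim 1 uptake effect, which is why the per-carrier figures should stay beside it.

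Optionally, add one later count for carriers, at a fixed time from randomisation in both arms. A clock starting at disclosure would begin later in UC and would not match the per-man comparison. At the planning figures this means contacting about seven men (4.6 + 2.0 = 6.6). It needs consent and IRB wording for contact beyond 3 months, and it must fit the one-year grant framework in section 2.0 and the 9/1/20 completion date in section 9.1. Section 25.1 foresees "data analysis and manuscript preparation continuing for 1 years after the completion of participant follow-up", but that year is set aside for analysis and writing, not for further follow-up. Aim 3 would then report later than the other aims.
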